5.4.4. Criteria for Permanent Discontinuation of Study Drug

The occurrence of unacceptable toxicity not caused by the underlying malignancy will be presumed to be related to study drug treatment and will require that the study drug be permanently discontinued. Unacceptable toxicity is defined as follows:

- Occurrence of an AE that is related to treatment with the study drug that, in the judgment of the investigator or the sponsor's medical monitor, compromises the subject's ability to continue study-specific procedures or is considered to not be in the subject's best interest.
- An AE requiring more than 2 dose reductions.
- Persistent AE requiring a delay of therapy for more than 21 days unless a greater delay has been approved by the sponsor.
- Increase in QT/QTcF to > 500 milliseconds or to > 60 milliseconds over baseline. In case of a QTc > 500 milliseconds, the subject must be hospitalized and a continuous ECG monitoring must be set up until the measure of the QTc interval decreases below 500 milliseconds and until acceptable in the opinion of a local cardiologist.

5.5. Withdrawal of Subjects From Study Treatment

5.5.1. Withdrawal Criteria

Subjects **must** be withdrawn from study treatment for the following reasons:

- The subject becomes pregnant.
- Consent is withdrawn. Note Subjects may choose to discontinue study treatment and remain in the study to be followed for progression and survival.
- Further treatment would be injurious to the subject's health or well-being, in the investigator's medical judgment. Subject would still be followed for progression and survival.
- The study is terminated by the sponsor.
- The study is terminated by the local health authority, IRB, or IEC.
- Unacceptable toxicity has occurred.
- Disease progression has been reported.
- Other antineoplastic treatment is initiated.

A subject **may** be discontinued from study treatment as follows:

- If, during the course of the study, a subject is found not to have met eligibility criteria but is receiving clinical benefit as per the investigator, the medical monitor, in collaboration with the investigator, will determine whether the subject should be withdrawn from the study. This includes cases where the local genomic testing result is positive for an FGF/FGFR alteration but the central genomic testing is not.
- If a subject is noncompliant with study procedures or study drug administration in the investigator's opinion, the sponsor should be consulted for instruction on handling the subject.

5.5.2. Withdrawal Procedures

In the event that the decision is made to permanently discontinue the study drug, the subject will be withdrawn from the study and the end-of-treatment visit should be conducted. Reasonable efforts should be made to have the subject return for a follow-up visit. These visits are described in Section 6. The last date of the last dose of study drug and the reason for subject withdrawal will be recorded in the eCRF.

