5.6. Withdrawal of Subjects From Study

If the subject discontinues study treatment and actively withdraws consent for collection of follow-up data (safety follow-up or disease assessment), then no additional data collection should occur; however, subjects will have the option of withdrawing consent for study treatment but continuing in the follow-up period of the study for safety/efficacy assessments.

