6.4.2. Disease Status Follow-Up

Subjects who discontinue study treatment for a reason other than disease progression will move into the disease status follow-up period and should be assessed every 9 weeks by radiologic imaging to monitor disease status. Every effort should be made to collect information regarding disease status until:

- The start of new antineoplastic therapy.
- Disease progression.
- Death.
- The end of the study.

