6.4.3. Survival Follow-Up

Once a subject has received the last dose of study drug, confirmed disease progression, or starts a new anticancer therapy, the subject moves into the survival follow-up period and should be contacted by telephone, email, or visit at least every 12 weeks to assess for survival status until death, withdrawal of consent, or the end of the study, whichever occurs first.

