7.3.2. Progression-Free Survival

Progression-free survival is defined as the length of time from the start of the study drug (Day 1) until the earlier of death or PD by RECIST v1.1 as assessed by the independent centralized

radiological review committee. The date of PD will be the timepoint at which progression is first recorded. Censoring for PFS will follow the algorithm outlined in [Table 1](#), which is based on the FDA Guidance for Industry: Clinical Trial Endpoints for the Approval of Cancer Drugs and Biologics ([FDA 2015](#), [FDA 2018](#))

The number of subjects who progressed or died and the number of subjects censored will be summarized. The Kaplan-Meier estimate of median PFS will be presented with its 95% CI. The 95% CI will be calculated using the Brookmeyer and Crowley's method ([Brookmeyer and Crowley 1982](#)). The PFS analysis will be conducted for Cohorts A, B, and C, respectively.

Progression-free survival for Cohort A will be analyzed for each subgroup as described in Section [7.2.2](#), with the exception of renal/hepatic impairment. If there are sufficient subjects in each subgroup, forest plots of median PFS and its 95% CI for each subgroup will be provided.

Table 1: Evaluation and Censoring of Progression-Free Survival

Situation	Outcome	Date of Progression or Censoring
No baseline tumor assessment	Censored	Day 1
No adequate postbaseline response assessment	Censored	Day 1
Progression documented between scheduled response assessments	Progressed	Date of first overall response of progressive disease
No progression	Censored	Date of last adequate response assessment (not NE and not missing)
Study discontinuation for undocumented progression	Censored	Date of last adequate response assessment (not NE and not missing)
Study discontinuation for toxicity or other reason	Censored	Date of last adequate response assessment (not NE and not missing)
New anticancer treatment started	Censored	Date of last adequate response assessment (not NE and not missing) prior to starting of the new anticancer treatment
Death before first progressive disease assessment	Progressed	Date of death
Death between adequate assessment visits	Progressed	Date of death
Death or progression after more than 1 missed assessment	Censored	Date of last adequate response assessment (not NE and not missing)

NE = not evaluable.

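### Protocol 5.5.2 withdraws a subject from the study, not just from treatment, when study drug stops; this contradicts 4.4, 5.5.1, 5.6, 6.4 and 7.6 and, if followed literally, ends follow-up that OS, PFS and DOR need

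*Protocol*

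**What the plan says.** Protocol 5.5.2 sets the site procedure for the case where the decision is to "permanently discontinue the study drug, the subject will be withdrawn from the study and the end-of-treatment visit should be conducted". No reason for stopping is exempted. The section then adds "Reasonable efforts should be made to have the subject return for a follow-up visit", points to Section 6, and has the site record the last-dose date and the reason for withdrawal in the eCRF.

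Other Protocol sections treat drug stop as the start of follow-up:

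- **4.4:** when drug is discontinued, the treatment period ends and follow-up begins.
- **5.5.1, consent bullet:** "Subjects may choose to discontinue study treatment and remain in the study to be followed for progression and survival".
- **5.5.1, bullet on treatment judged injurious:** "Subject would still be followed for progression and survival".
- **5.6:** data collection ends only when the subject actively withdraws consent for it; otherwise "subjects will have the option of withdrawing consent for study treatment but continuing in the follow-up period of the study for safety/efficacy assessments".
- **6.4.2:** "Subjects who discontinue study treatment for a reason other than disease progression will move into the disease status follow-up period", with imaging every 9 weeks.
- **6.4.3:** "Once a subject has received the last dose of study drug, confirmed disease progression, or starts a new anticancer therapy", survival contact follows at least every 12 weeks until the subject dies, withdraws consent or the study ends.
- **7.6.1 and 7.6.4:** imaging continues after a non-progression stop, and survival data continue to be collected.

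The SAP separates the two kinds of stopping. Section 6.2 tabulates treatment discontinuation and study discontinuation, each with its own reason. In 7.3.2, Table 1 has a row headed "Study discontinuation for toxicity or other reason" and a parallel row for undocumented progression. Both censor PFS at the last adequate response assessment, and 7.3.3 applies the same algorithm to DOR.

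**The concern.** Section 5.5.2 is the operative instruction: it says what the site does and records when drug stops. Read on its own, it turns every permanent drug stop into a study withdrawal, which 5.6 reserves for subjects who refuse further data collection.

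Treatment must stop at progression (5.5.1), while OS runs to death from any cause, so most deaths should come after drug stop. Whether they are observed depends on the survival contact in 6.4.3. PFS and DOR depend in the same way on the imaging in 6.4.2 for subjects who stop before progression. All three are secondary endpoints for every cohort, and survival contacts or scans that are missed may not be recoverable later.

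**Working it through.** The plan attaches no figure to this point, so there is none to reproduce. The check compares what each endpoint would receive under the two readings.

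| Endpoint | 5.5.2 taken literally | 4.4, 5.6 and 6.4 |
|---|---|---|
| OS | Contact ends at about the end-of-treatment or safety visit | Contact at least every 12 weeks |
| PFS, DOR (stop without progression) | No scans after the end-of-treatment assessment | Scans every 9 weeks until progression, new therapy, death or end of study |
| ORR | No confirming scan after drug stop | Confirming scan possible during follow-up |

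**OS.** SAP 7.3.5 censors at the earlier of the last-known-alive date and the data cut-off. Last known alive is the later of the last study visit and the dates on the Survival Follow-Up and Subject Status eCRFs. Coding a drug stop as study withdrawal therefore does not censor OS by itself. If survival contact really ceases, however, the last study visit becomes the censoring date, close to the end of treatment.

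An illustration of what could be lost, under assumptions that are not in the documents: survival after drug stop is exponential with median m months, and contact ends 35 days after drug stop (6.4.1 puts the safety visit 30 to 35 days after the end-of-treatment visit). With SAP 6.4's month of 30.4375 days, the window is w = 35 / 30.4375 = 1.15 months. The share of post-stop deaths inside it is 1 − exp(−ln 2 × w / m):

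| m (months) | Share of post-stop deaths observed |
|---|---|
| 3 | 23% |
| 6 | 12% |
| 9 | 8% |
| 12 | 6% |

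This applies only to subjects whose site actually stopped contact.

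**PFS and DOR.** Subjects whose progression has already been assessed centrally have had their event and are unaffected. A subject who stops for toxicity and is recorded as having left the study fits the Table 1 row headed "Study discontinuation for toxicity or other reason" and is censored at the last adequate assessment. The documents do not give the share stopping without progression. If it is assumed to be 5% to 15%, that is 100 × 0.05 = 5 to 100 × 0.15 = 15 of the 100 planned Cohort A subjects. This is an upper limit that is reached only if every site followed 5.5.2 literally.

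**ORR.** SAP 7.2.1 requires confirmation of CR and PR and keeps inadequately assessed subjects in the denominator. Only a subject who stops drug between a first response and its confirming scan could be affected.

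**The case against.** The strongest reply is that context largely cures the phrase. Section 5.5.2 sits under a heading about withdrawal from study treatment, withdrawal from the study has its own section (5.6), and 5.5.2 itself asks for a follow-up visit and points to Section 6. A site would have to follow one clause against the synopsis, Table 5 and at least six other sections. The summary of Amendment 2 in Appendix E also records an aim that subjects may stop treatment and stay on study. All of this stands as evidence of intent, and it makes widespread loss of follow-up unlikely. It does not remove the contradiction from the current procedure.

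Three stronger readings are tempting, and the documents do not support them.

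- **That 6.4.2 and 6.4.3 also conflict, because both claim the subject at last dose.** The synopsis lists imaging every 9 weeks and survival contact every 12 weeks after discontinuation. Table 5 has a column for each, and 7.6.4 has sites supply tumour assessments during survival follow-up for subjects who stopped for a reason other than progression. The two run in parallel. Moving the survival trigger away from last dose would contradict the synopsis and the Table 5 note.
- **That subjects stopping for toxicity will be censored for PFS and DOR.** The Table 1 rows refer to study discontinuation, which SAP 6.2 counts separately from treatment discontinuation. As worded, they do not apply to a subject still being imaged under 6.4.2.
- **That median OS, PFS and DOR are biased upward.** For OS this is plausible where contact truly ends, because drug stops at progression and subjects would be censored as their prognosis worsens. For PFS and DOR, nothing in the documents shows whether subjects who stop for toxicity progress sooner or later than the rest.

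**Conclusion.** The contradiction is real and sits in an instruction that sites act on. It is most likely a drafting slip for withdrawal from study treatment. Harm follows only where a site takes it literally and ends contact or imaging. There, OS would be censored near the end of treatment, and PFS and DOR could be censored at the last adequate assessment in subjects without centrally assessed progression; that censoring may be informative.

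The documents do not say how many sites or subjects this would involve, so no overall size can be given. The 6% to 23% and the 5 to 15 subjects above are illustrations under stated assumptions. The primary ORR analysis is largely untouched, and the SAP states no efficacy hypothesis (7.1), so no formal test depends on these endpoints. The point is worth correcting because the remedy is nearly free; it does not threaten the primary result.

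**What to change.** Reconcile 5.5.2 with its parent heading and with 4.4, 5.5.1, 5.6, 6.4, 7.6.1 and 7.6.4. Change the clause so that the subject is withdrawn from study treatment rather than from the study. Add a sentence saying that the subject then enters the follow-up described in Section 6.4, unless consent for follow-up is withdrawn under 5.6.

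Optionally, add a note to SAP Table 1 that the study-discontinuation rows apply only when tumour follow-up has ended, not at treatment discontinuation alone. The survival follow-up trigger in 6.4.3 needs no change.

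The cost is one phrase and one sentence in the Protocol, plus one optional note in the SAP. No visit, scan or contact is added, because the follow-up is already planned, and no rule on when treatment stops is altered.

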5.6. Withdrawal of Subjects From Study

If the subject discontinues study treatment and actively withdraws consent for collection of follow-up data (safety follow-up or disease assessment), then no additional data collection should occur; however, subjects will have the option of withdrawing consent for study treatment but continuing in the follow-up period of the study for safety/efficacy assessments.

5.7. Concomitant Medications

5.7.1. Restricted Medications

The use of mild or moderate CYP3A4 inhibitors and OCT2 substrates, such as metformin, should involve careful monitoring in relation to safety.

Calcium-based phosphate binding medications should not be used due to a concern for soft tissue mineralization.

5.7.2. Prohibited Medications

The following medications and measures are prohibited:

- The concomitant administration of potent CYP3A4 inhibitors and inducers and moderate CYP3A4 inducers. Based on the low overall bioavailability of topical ketoconazole, there are no restrictions on topical ketoconazole. See [Appendix B](#) for a list of potent CYP3A4 inhibitors and inducers.
- Any concomitant use of a selective FGFR inhibitor (other than the study drug)
- Investigational study drug for any indication.
- Use of any anticancer medications other than the study medication.

6. STUDY ASSESSMENTS

All study assessments will be performed as indicated in the schedule of assessments ([Table 5](#)), and all laboratory assessments will be performed as indicated in [Table 6](#).

[Table 7](#) presents a summary of clinical laboratory analytes to be assessed. The order of assessments is suggested by the order of mention within the schedule. See Section 7 for instructions on each assessment. Further details of study procedures and assessments can be found in the study reference manual.

Table 5: Study Assessments

Procedure	Protocol Section	Pre-screening	Screening	Treatment				EOT	Follow-Up			Notes
				Days -28 to -1	Cycle 1		Cycle 2+		Safety	Disease Status	Survival	
			Day 1		Day 8 (± 3 days)	Day 15 (± 3 days)	Day 1 (± 3 days)					
			EOT + 30 (+5) days		Every 9 weeks	Every 12 weeks						
Genomic testing	7.1	X	X*								* May be done during prescreening or during screening.	
Informed consent	7.1	X	X									
Eye examination (includes slit lamp, visual acuity, funduscopy with digital imaging, and OCT)	7.5.5		X				X*	X				* Eye examination to be performed every 3 cycles (± 14 days) starting with Cycle 3 and/or as clinically indicated.
Review inclusion and exclusion criteria	3		X	X								
Demography and medical history	7.3		X									
Prior/concomitant medications	7.4		X	X	X	X	X	X	X			
Physical examination/ body weight, height	7.5.2		X*	X	X	X	X	X	X			* Comprehensive examination at screening, targeted physical examination thereafter.
Vital signs	7.5.3		X	X	X	X	X	X	X			
12-lead ECG	7.5.4		X	X		X	X	X	X			
ECOG status	7.6.2		X	X	X	X	X	X	X			

Table 5: Study Assessments (Continued)

Procedure	Protocol Section	Pre-Screening	Screening	Treatment				EOT	Follow-Up			Notes
				Days -28 to -1	Cycle 1		Cycle 2+		Safety	Disease Status	Survival	
			Day 1		Day 8 (± 3 days)	Day 15 (± 3 days)	Day 1 (± 3 days)					
			EOT + 30 (+5) days		Every 9 weeks	Every 12 weeks						
CT or MRI	7.6.1		X				X*	X		X**		* Every 2 cycles through Cycle 4; every 3 cycles thereafter starting with Cycle 7. ** Subjects who discontinue study treatment for a reason other than disease progression.
Review AEs	7.5.1		X	X	X	X	X	X	X			
Survival status	7.8.2										X*	* Once a subject has received the last dose of study drug, confirmed disease progression, or starts a new anticancer therapy.

CT = computed tomography; MRI = magnetic resonance imaging.

Table 6: Laboratory Assessments

	Protocol Section	Prescreening	Screening	Treatment				EOT	Follow-Up	Notes
				Cycle 1			Cycles 2+			
				Day 1	Day 8 (± 3 Days)	Day 15 (± 3 Days)				
Serum chemistries	7.5.6		X	X*	X	X	X	X	* May be performed within 3 days of the first dose.	
Hematology	7.5.6		X	X*	X	X	X	X	* May be performed within 3 days of the first dose.	
Lipid panel	7.5.6			X				X		
Endocrine	7.5.6		X	X			X	X		
Coagulation panel	7.5.6		X				X*	X	* Only every 3 cycles starting at Cycle 3.	
Hepatitis screening	7.5.6.2		X							
Urinalysis	7.5.6		X				X*		* Only every 3 cycles starting at Cycle 3.	
Pregnancy test	7.5.6.1		X*	X**			X**	X**	* Serum ** Day 1 of each cycle; urine pregnancy test allowed.	
HIV testing	7.5.6.3		X*						* Optional for US subjects.	
Central laboratory										
Blood sample for PK	7.7				X*					Samples will be drawn at predose, 1-2 hours postdose, and 4-12 hours postdose (3 samples total). *Subject must fast 8 hours before first sample (predose).
Tumor tissue sampling/archival tissue	7.8	X*					X**			* Slides or FFPE block must be provided. ** Optional on-treatment or EOT biopsy, such as disease progression after complete or PR.

Table 7: Laboratory Tests: Required Analytes

Serum Chemistries	Hematology	Urinalysis With Microscopic Examination	Hepatitis Screening	Coagulation
Albumin Alkaline phosphatase ALT AST Bicarbonate (not in Japan) Blood urea nitrogen or urea Calcium Chloride Creatinine Glucose Lactate dehydrogenase Phosphate Potassium Sodium Total bilirubin Direct bilirubin (if total bilirubin is elevated above ULN) Total protein Uric acid Vitamin D (25-hydroxyvitamin D and 1,25-dihydroxyvitamin D)	Complete blood count, including: Hemoglobin Hematocrit Platelet count Red blood cell count White blood cell count Differential count, including: Basophils Eosinophils Lymphocytes Monocytes Neutrophils Absolute values must be provided for: WBC differential laboratory results: Lymphocytes Neutrophils	Color and appearance pH and specific gravity Bilirubin Glucose Ketones Leukocytes Nitrite Occult blood Protein Urobilinogen	Hepatitis B surface antigen Hepatitis B surface antibody Hepatitis B core antibody HCV antibody NOTE: If any of the above are positive, HBV-DNA, HCV-RNA to assess risk of reactivation.	PT PTT or aPTT INR
		Lipid Panel	Other	Pregnancy Testing
		Total cholesterol Triglycerides LDL HDL	Endocrine- parathyroid hormone HIV testing (optional for US subjects)	Female subjects of childbearing potential only require a serum test at screening and a urine pregnancy test before the first dose on Day 1 of every cycle before dose administration and at EOT. Pregnancy tests (serum or urine) should be repeated if required by local regulations.

HDL = high-density lipoprotein; INR = international normalized ratio; LDL = low-density lipoprotein; PT = prothrombin time; PTT = partial thromboplastin time; WBC = white blood cell.

Note: Additional tests may be required, as agreed by investigator and sponsor, based on emerging safety data.

6.1. Prescreening and Screening

Prescreening is available for subjects without a genomic testing report (results within approximately 2 years of screening are valid for this study). Prescreening allows genomic testing to be performed outside of the 28-day screening window.

Screening is the interval between signing the ICF and the day that the subject is enrolled in the study (Cycle 1 Day 1). Screening may not exceed 28 days. Assessments that are required to demonstrate eligibility may be performed over the course of 1 or more days during the screening process.

Procedures conducted as part of the subject's routine clinical management (eg, blood count, imaging study) and obtained before signing of informed consent may be used for screening or baseline purposes provided that the procedure meets the Protocol-defined criteria and has been performed in the time frame of the study (ie, within 28 days of Cycle 1 Day 1). All information associated with eligibility requirements must be entered into the appropriate eCRF pages.

Results from the screening visit evaluations will be reviewed to confirm subject eligibility before enrollment or the administration of study drug. Tests with results that fail eligibility requirements may be repeated once during screening if the investigator believes the results to be in error. For screening assessments that are repeated, the most recent available result before treatment assignment will be used to determine subject eligibility. Treatment should start as soon as possible, but within 3 days after the date of enrollment. Additionally, a subject who fails screening may repeat the screening process 1 time if the investigator believes that there has been a change in eligibility status (eg, after recovery from an infection). Subjects who are rescreened will receive a new subject number through the IRT.

